## 6.6. Meals and Dietary Requirements

Each dose of venetoclax should be taken with approximately 240 mL of water within 30 minutes after the completion of a meal, preferably breakfast.

Subjects should not consume grapefruit or grapefruit products, Seville oranges, or Star fruit within the 3-day period prior to the first DS-1594b or venetoclax administration and until the last day of DS-1594b or venetoclax is completed due to possible CYP3A-mediated metabolic interaction.

## 6.7. Modifications of Dose Schedules Other Than the Above Will Be Allowed Within the Following Guidelines

- Dose adjustments by more than 1 dose level at a time for azacitidine or venetoclax (e.g., from azacitidine  $75\text{ mg/m}^2$  to  $25\text{ mg/m}^2$ ) can be considered when judged in the best interest of the subject (e.g. severe myelosuppression) when toxicity has resolved. The reason for this reduction will be discussed with the PI or Co-PI and documented in the medical record.
- A subject who has had a dose reduction because of any of the reasons mentioned above may have their dose escalated provided the subject has remained free of

toxicity requiring dose adjustments as defined above in [Table 11](#)[Table 11](#) for at least 1 month. Escalation will be made by 1 dose-level increment only, and not more frequent than every month. The dose of any agent must not exceed the RP2D dose for that agent in this protocol (i.e. azacytidine dose cannot exceed 75mg/m^2 x 7 days, venetoclax dose cannot exceed 400 mg/day, and established RP2D for DS-1594b from Phase 1).

Formatted: C-Hyperlink

- Treatment interruptions and dose modifications other than the ones mentioned above can be considered after discussion with the PI and proper documentation of the rationale. This includes delays in chemotherapy cycles because of persistent myelosuppression, other side effects, subject request, or other reasons. Missed doses of DS-1594b do not need to be made up. Dose adjustment/delay/interruptions of only one of the agents is permissible if the toxicity is most likely judged to be related to one of the agents by the investigator (e.g., in subjects with Differentiation Syndrome ([Table 13](#)[Table 13](#)) this would be likely secondary to the DS-1594b, in subjects with neutropenia this would be likely secondary to azacitidine and venetoclax). Subjects in whom one agent is interrupted/discontinued for potential toxicity may be able to continue treatment on protocol if it is in the best interest of the subject to continue on protocol.

Formatted: C-Hyperlink

## 6.8. Treatment Interruptions

Treatment interruptions and dose modifications or delays other than the ones mentioned above can be considered after discussion with the PI or Co-PI and clear documentation of the rationale in the medical records.

## 6.9. Intra-Patient Dose Escalation (IPDE)

Intra-patient dose escalation (IPDE) of DS-1594b is permitted for subjects enrolled in the dose escalation portion of the study who may benefit from IPDE after approval from the PI or Co-PI, provided the subject meets all of the following criteria:

- The subject has failed to achieve a complete remission (CR) or has experienced disease progression on treatment with DS-1594b,
- The subject has not experienced a DLT or treatment related adverse event requiring DS-1594b dose reduction or interruption.

The dose may be escalated up to a dose level that has previously been established to be safe and tolerable in at least 3 DLT evaluable subjects (for example, a subject enrolled at 50mg BID may be dose escalated to 70mg BID only after the 70mg BID dose level has been declared safe and tolerable in at least 3 DLT evaluable subjects).

Additionally, a subject may be switched to an alternative DS-1594b dosing regimen (BID vs. QD) once they have completed the DLT evaluation period in Phase I, if that dosing regimen has been found to be safe and tolerable in at least 3 DLT evaluable subjects (for example, from 50 mg BID to 100 mg QD).

## 7. AGENT FORMULATION AND PROCUREMENT

### 7.1. Potential Indications and Use

DS-1594b is being developed for the treatment of relapsed or refractory AML or ALL with MLL1-r or AML with NPM1-mutations.

### 7.2. Ongoing Clinical Trials

This is the first clinical study for DS-1594b. There are no other ongoing studies.

### 7.3. Dosing and Administration

See Section 5.1.2 for DS-1594b dosing and administration information.

### 7.4. Packaging and Labeling

DS-1594b is packaged as 35 tablets per bottle, in high-density polyethylene (HDPE) bottles with desiccant. The labeling complies with the requirements of the applicable regulatory agencies.

### 7.5. Study Drug Description and Preparation

DS-1594b tablets are formulated in 3 strengths: 20 mg, 50 mg, and 200 mg. The dose strength of the tablet is expressed as the free form of DS-1594b. DS-1594b tablets are supplied as grayish-red, film-coated round-shaped tablets (20 mg) and grayish-red, film-coated oblong-shaped tablets (50 mg and 200 mg).

DS-1594b is supplied as tablets that need no further preparation at the study sites.

### 7.6. Study Drug Storage

DS-1594b must be stored appropriately in a locked cabinet/room with limited and controlled access under the recommended storage conditions. The required storage conditions are provided in the investigational medicinal product labeling.

*NOTE: If storage conditions go outside of the recommended storage conditions, the Study Center must not dispense the affected supplies (affected supplies should be placed in quarantine). Proper notification processes must be followed immediately after receipt of DS-1594b identified as having a temperature excursion.*

### 7.7. Study Drug Accountability

A Drug Accountability Record must be kept current and must contain the dates and quantities of study drug received, the subject's identification number and/or initials or supply number (as applicable), the date and quantity of DS-1594b dispensed and remaining (in tablets), as well as the initials of the dispenser.

**Azacitidine:** It is commercially available and will be handled as per the packet insert and standards in the site pharmacy.

**Venetoclax:** It is commercially available and will be handled as per the packet insert and standards in the site pharmacy

International Non-proprietary name venetoclax (formerly ABT-199)

Manufacturer Abbvie/Genentech

Dose 70 - 400 mg daily

Route of Administration oral

Formulation Capsule formulation (10 mg, 50 mg and 100 mg)

Venetoclax will be obtained from commercial source. For further details, please refer to the prescribing information (Appendix G).

**Mini-HCVD:** It is commercially available and will be handled as per the packet insert and standards in the site pharmacy. cyclophosphamide, vincristine, methotrexate, cytarabine, rituximab, MESNA, filgrastim, peg-filgrastim, dexamethasone, and prednisone will be obtained from commercial source. Biosimilars may be used for filgrastim or peg-filgrastim. For further details on each drug, please refer to the prescribing information .

**Disposition of unused drug:** all unused drug will be disposed of per institutional guidelines and procedures.

Variations in infusion times of drugs due to minor differences in IV bag overfill/under fill and institutional procedure on flushing chemotherapy lines will not result in protocol deviation. All infusion times are considered approximate.

For further details on drug formulation, reconstitution, administration, infusion related instructions, concern and plan of management for infusion related topics please the respective agents IB or package insert.

## 8. SUBJECT EVALUATION

Every effort will be made to adhere to the schedule of events and all protocol requirements.

### 8.1. Schedule of Assessments

All Assessment Schedule Tables are in the Appendix:

Phase 1	Dose Escalation	Table 32 Table 32
Phase 2	Cohorts A & B	Table 33 Table 33
	Cohort C	Table 34 Table 34
	Cohort D	Table 35 Table 35

Formatted: C-Hyperlink

Formatted: C-Hyperlink

Formatted: C-Hyperlink

Formatted: C-Hyperlink

## 8.2. Screening

The Screening period begins up to 14 days prior to treatment. It is anticipated that subjects will recently have had some, or all, of the screening tests done as part of routine care outside the auspices of this study. Results of some tests done as part of routine care, outside the auspices of this study, may be used to qualify the subject. All pretreatment studies should be obtained within 14 days of first dose, unless otherwise stated. Written informed consent must be obtained before any study-specific procedure is performed.

All study procedures, risks, and benefits must be explained to the subject and/or their legal guardians; the Study Informed Consent Form must be reviewed with the subject and/or their legal guardians; all the subject's and/or their legal guardians' questions must be answered; the subject and/or their legal guardians must sign the Informed Consent Form. Subjects and/or their legal guardians must receive a copy of their Informed Consent Form.

All subjects will be assigned a unique identification number upon signing the informed consent form.

At screening, the following will be performed:

- A complete history and physical, medical and acute leukemia disease history (including classification per the latest WHO criteria for AML or ALL), disease state (primary refractory, untreated relapse, refractory relapse), number of prior lines of therapy, best response to most recent line of therapy, duration of most recent remission (if applicable), prior medications, non-drug therapies, and radiotherapy within 28 days of Cycle 1 Day 1, prior transfusions (red blood cell and platelet) within 28 days of Cycle 1 Day 1, concomitant medications, non-drug therapies, and radiotherapy, and performance status.
- Complete blood count (CBC), platelet count, differential (differential can be omitted if WBC is  $\leq 0.4 \times 10^9/L$ ), and international normalized ratio (INR).
- Serum chemistry panel (including creatinine, electrolytes, glucose, uric acid, calcium, magnesium, BUN).
- Hepatic panel (AST, ALT, Alk phosphatase, total bilirubin [fractionated])
- Creatinine Kinase (fractionated if  $> ULN$ )
- Troponin
- Alpha-Melanocyte stimulating hormone (alpha-MSH)
- Fasting morning adrenocorticotrophic hormone (ACTH), aldosterone, renin, and cortisol levels. If results are abnormal, consult an endocrinologist. Perform an ACTH stimulation test if adrenal insufficiency is suspected.
- Urinalysis (by dipstick) to include appearance, bilirubin, blood, specific gravity, glucose, ketones, pH, and protein.
- Pregnancy test (urine or plasma) in females of childbearing potential should be performed within 72 hours before initiation of protocol therapy.

- Bone marrow aspirate/biopsy
  - Cytogenetics and molecular tests for MLLr or NPM1m performed by MDACC laboratories must be obtained
- Height, weight, and BSA calculated by the Mosteller formula.
- HIV antibody test (if required by local regulations)
- Hepatitis B (HBsAG) test, and Hepatitis C antibody test
- Blood oxygen levels (SpO2).
- Vital signs, including blood pressure, pulse rate, respiratory rate, and temperature (taken 5 min prior to the electrocardiogram [ECG]).
- Triplicate Electrocardiogram (ECG) by 12-lead or Holter measurement at baseline. See Section 8.5 for the details of ECG monitoring.
- Pretreatment correlative studies (Section 8.6).
- MUGA or Echocardiogram

### 8.3. Evaluation During Treatment

- Physical exam at the start of each cycle ( $\pm$  4 days).
- Hematology/coagulation labs: CBC with differential, platelet count, INR pre-dose on Cycle 1, Day 1 and at least 3 times per week for the first cycle, then 2 times per week for Cycles 2 and 3, then one to two times per week in subsequent cycles (differential can be omitted if WBC is  $\leq 0.5 \times 10^9/L$ ). Lower frequency of laboratory evaluations may be considered on a case by case basis after Cycle 6 in subjects in remission, after discussion and approval from PI (e.g, at least once every 2 weeks).
- Serum chemistry labs: serum creatinine, electrolytes, glucose, uric acid, calcium, magnesium, BUN pre-dose on Cycle 1, Day 1 and at least 3 times per week for the first cycle, then 2 times per week for Cycles 2 and 3, then one to two times per week in subsequent cycles. Lower frequency of laboratory evaluations may be considered on a case by case basis after Cycle 6 in subjects in remission, after discussion and approval from PI (e.g, at least once every 2 weeks)
- Hepatic labs: AST, ALT, alkaline phosphatase, total bilirubin, direct bilirubin, and indirect bilirubin pre-dose on Cycle 1, Day 1 and at least 3 times per week for the first cycle, then 2 times per week for Cycles 2 and 3, then one to two times per week in subsequent cycles. Lower frequency of laboratory evaluations may be considered on a case by case basis after Cycle 6 in subjects in remission, after discussion and approval from PI (e.g, at least once every 2 weeks).
- Creatinine kinase (fractionated if  $>$  ULN) pre-dose on Cycle 1, Day 1 and at least once weekly in Cycles 1-3, then monthly. Lower frequency of laboratory evaluations may be considered on a case by case basis after Cycle 6 in subjects in remission, after discussion and approval from PI.

- Urinalysis pre-dose on Cycle 1, Day 1 and monthly during treatment.
- Pregnancy test (urine or plasma) in females of childbearing potential should be performed monthly during treatment.
- Tumor lysis syndrome chemistry tests (potassium, uric acid, creatinine, calcium and phosphorus) will be obtained same day prior to dosing and 5-8 hours on each day after a new venetoclax dose during cycle 1 (Cohort C).
- Troponin during treatment as clinically indicated.
- Plasma alpha-melanocyte stimulating hormone (alpha-MSH), fasting morning adreno-corticotrophic hormone (ACTH), aldosterone, renin, and cortisol levels on Cycle 1 Day 28 ( $\pm$  4 days), then once every 3 cycles beginning at Cycle 3 (eg, Cycles 3, 6, 9) and at End of Treatment. If results are abnormal, consult an endocrinologist. Perform an ACTH stimulation test if adrenal insufficiency is suspected.
- Bone marrow aspiration/biopsy on Cycle 1 Day 28 ( $\pm$  4 days), then on Day 28 ( $\pm$  4 days) of Cycles 2, 3, 6, 9 and progression. Bone marrow tests can be ordered more frequently if mandated by development of peripheral blood counts. No repeat bone marrow is necessary if nonresponse or progressive disease can be unequivocally diagnosed from peripheral blood tests or, in subjects with a WBC  $<$  0.3 if the bone marrow test is considered noncontributory by the investigator at any time point. For subjects in Cohort C, the initial bone marrow aspiration/biopsy in Cycle 1 will be on Day 21 ( $\pm$  4 days).
- For subjects that remain on study with no significant toxicity for more than 6 months, subsequent evaluations during study may be modified after discussion with the principal investigator. These include a decrease in frequency of bone marrow aspiration and biopsy to every 6-12 months (or as clinically indicated), correlative studies to every 6-12 months (or suspension of sample collection for correlative studies), other laboratory tests to once every cycle.

#### 8.4. PK Assessment

Blood samples for PK analysis of DS-1594b and metabolites (if appropriate) will be collected during the study from all subjects receiving DS-1594b. PK parameters using standard non-compartmental method will be generated. Plasma concentration-versus-time data will be summarized using summary statistics by dose/study day/time

- On Cycle 1 Day 1 (dose escalation and dose expansion): Cmax, Tmax, Tlast, AUClast, AUCtau, AUCinf\*, Kel\*, t1/2\*, CL/F\*, Vz/F\*
- On Cycle 1 Day 8 (dose escalation and dose expansion): Cmax, Cavg, Ctrough, Tmax, Tlast, AUClast, AUCtau, Kel\*, t1/2\*, CLss/F, Vz/F\*, AR\*\*, t1/2,ar\*\*\*
- Food effect sub-study:
  - On Cycle 1 Day 1: Cmax, Tmax, Tlast, AUClast, AUCtau, AUCinf\*, Kel\*, t1/2\*, CL/F\*, Vz/F\*

- On Cycle 1 Day 8 and Cycle 1 Day 15: Cmax, Ctrough, Tmax, Tlast, AUClast, AUCltau, Kel\*, t1/2\*, CLss/F, Vz/F\*
- DDI sub-study:
  - On Cycle 1 Day 1: Cmax, Tmax, Tlast, AUClast, AUCltau, AUCinf\*, Kel\*, t1/2\*, CL/F\*, Vz/F\*
  - On Cycle 1 Day 8 and Cycle 1 Day 18 (or Cycle 2 Day 10 for subjects who enrolled to sub-study prior to MTD/RP2D determination): Cmax, Ctrough, Tmax, Tlast, AUClast, AUCltau, Kel\*, t1/2\*, CLss/F, Vz/F\*

\*: To be calculated only if possible.

\*\*: Accumulation ratio (AR) calculated as AUCltau at steady state /AUCltau following first dose, where tau is the dosing interval of 12 hour

\*\*\* Effective half-life can be calculated from AR:  $\ln 2 \cdot \tau / \ln(AR / (AR-1))$

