### 3.1. Rationale for dose and regimen selection

The selection of the starting dose level and regimen is based on the extrapolation of data from cell line efficacy models and toxicology studies in rodents and monkeys.

The DS-1594b Severely Toxic Dose in 10% of animals (STD10) in mice was greater than 300 mg/kg/day and the Highest Non-Severely Toxic Dose (HNSTD) in monkeys was 60 mg/kg/day. The human equivalent dose (HED) of 300 mg/kg/day in mice, based on allometric scaling by body surface area, is approximately 24.3 mg/kg, and using 1/10th of the HED gives a dose of 2.4 mg/kg as the recommended starting human dose for the proposed clinical study. The value of 2.4 mg/kg is lower than a starting dose (3.2 mg/kg) derived from 1/6th of the HED for the HNSTD (60 mg/kg/day) in monkeys. The estimated human systemic exposure at the starting dose exceeds the IC50 of DS-1594b against MV-4-11 human AML cell line (1.97 nM [1.13 ng/mL]), and inhibition of cell proliferation is expected. Therefore, the value of 2.4 mg/kg is considered the appropriate starting dose for the proposed clinical study. No supportive data are available at this stage that would suggest body size-based dosing would reduce human inter-subject variability in PK. Thus, based on an average body weight of 60 kg human, the recommended starting human dose is 140 mg/day. A dosing approach with 70 mg given twice a day will be adopted in order to reduce Cmax while maintaining AUC compared to once-daily dosing to mitigate potential QT interval prolongation risk, given the observed QTc interval prolongation signal seen in monkeys (see Section 2.4.2). In addition, the estimated clinical half-life of DS-1594b is ~ 7 to 8 hours, which also supports a twice daily dosing regimen.

Based on emerging clinical data to assess the PK and safety profile of DS-1594b, the frequency of dosing may be adjusted to once daily (QD), if deemed appropriate and supported by safety data. In this case, dose escalation would follow the same rules as the BID schedule. The SRC

may recommend the enrollment of simultaneous QD and BID dosing regimens or may switch from BID dosing to QD dosing.

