### 3.2. Phase 1 Design

The primary objective of Phase 1 is to determine the Maximum Tolerated Dose (MTD) and the Recommended Phase 2 Dose (RP2D) of DS-1594b when administered as a single agent in subjects with relapsed or refractory AML or ALL, including subjects with or without MLLr or NPM1m using a Bayesian optimal interval (BOIN) design to find the MTD.

The BOIN design is implemented in a simple way similar to the traditional 3+3 design but is more flexible and possesses superior operating characteristics that are comparable to those of the more complex model-based designs, such as the continual reassessment method (CRM).

At least 3 subjects must be enrolled at each dose level. If a dose level is found to be safe by the BOIN design we will escalate to the next higher dose level. The SRC can recommend additional enrollment of up to 9 additional subjects per dose level for dose levels that have already been deemed to be safe with the intent to gain additional information on safety, efficacy and PK at different dose levels, and to guide selection of optimal biologically effective RP2D. These additional 9 subjects per dose level will not be considered evaluable for DLTs. It is anticipated that approximately 18 subjects will be added in this Phase 1 expansion.

Although all R/R ALL and R/R AML subjects, irrespective of mutations, will be allowed during the Phase 1 dose-escalation the goal is to treat at least 3 subjects with MLLr or NPM1m are included at dose levels that are anticipated to be biologically active to allow for optimal evaluation of safety and efficacy in the presumed target population to guide selection of the optimal RP2D.

Treatment during Phase 1 dose escalation phase will follow continuous oral administration under a twice-daily schedule or daily schedule on a 28-day dosing cycle.

The first dose cohort will start at 70 mg twice daily, approximately every 12 hours. The target toxicity rate for the MTD is  $\phi = 0.2$  and the maximum sample size for determining the MTD is 42. Each cohort will include a minimum of 3 subjects. The DLT evaluation period will be limited to the first 28 days of dosing. DLTs are defined in Section 3.2.2 and only those DLTs that occur within the first cycle (28 days) will be used for dose finding. As shown in [Figure 2](#), the BOIN design uses the following rule, optimized to minimize the probability of incorrect dose assignment, to guide dose escalation/de-escalation:

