## 5. TREATMENT PLAN

### 5.1. Phase 1 Dose Administration

#### 5.1.1. Study Treatment

The orally administered film-coated tablet formulation of DS-1594b will be supplied by Daiichi Sankyo and are in 20 mg, 50 mg, and 200 mg dose strengths.

The first dose cohort will start at 70 mg twice daily, approximately every 12 hours. For provisional dose levels beyond the first dose cohort, see [Figure 1](#)[Figure 1](#). Alternative doses or dosing regimens may be enrolled based on emerging clinical data, including intermediate dose levels or dose de-escalation. BID and QD cohorts can be enrolled in parallel and will be evaluated independently for DLT.

Formatted: C-Hyperlink

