1	1	Post-dose 1h ( $\pm$ 10 min)
1	1	Post-dose 2h ( $\pm$ 10 min)
1	1	Post-dose 3h ( $\pm$ 10 min)
1	1	Post-dose 4h ( $\pm$ 10 min)
1	1	Post-dose 6h ( $\pm$ 10 min)
1	1	Post-dose 8h ( $\pm$ 10 min)
1	2	Pre-dose/0h b
1	5	Pre-dose/0h a
1	8	Pre-dose/0h a
1	8	Post-dose 0.5h ( $\pm$ 5 min)
1	8	Post-dose 1h ( $\pm$ 10 min)
1	8	Post-dose 2h ( $\pm$ 10 min)
1	8	Post-dose 3h ( $\pm$ 10 min)
1	8	Post-dose 4h ( $\pm$ 10 min)

Cycle	Day	Scheduled Time Point
1	8	Post-dose 6h ( $\pm$ 10 min)
1	8	Post-dose 8h ( $\pm$ 10 min)
1	9	Pre-dose/0h c
1	15	Pre-dose/0h a
1	15	Post-dose 2h ( $\pm$ 10 min)
1	15	Post-dose 4h ( $\pm$ 10 min)
1	15	Post-dose 6h ( $\pm$ 10 min)
1	15	Post-dose 8h ( $\pm$ 10 min)
1	16	Pre-dose/0h d
1	21	Pre-dose/0h a
1	21	Between 2-4 hours post-dose
2	1	Pre-dose/0h a
3	1	Pre-dose/0h a
4	1	Pre-dose/0h a
5	1	Pre-dose/0h a
6	1	Pre-dose/0h a
7	1	Pre-dose/0h a
8	1	Pre-dose/0h a
Unscheduled		Anytime
After intra-patient dose escalation (see Section 6.9):		
Cycle X of the new higher dose level or different dosing regimen (frequency)	8	Pre-dose/0h a
Cycle X of the new higher dose level or different dosing regimen (frequency)	8	Between 2-4 hours post-dose
Unscheduled		Anytime

All measurement times are relative to dose of DS-1594b unless otherwise specified.

a PK sample should be taken immediately prior to the next administration of DS-1594b.

b Predose C1D2 PK sample is the same as 24 hours ( $\pm$  2h) C1D1 post-dose PK sample; it will be collected immediately prior the administration of DS-1594b.

c Predose C1D9 PK sample is the same as 24 hours ( $\pm$  2h) C1D8 post-dose PK sample; it will be collected immediately prior the administration of DS-1594b.

d Predose C1D16 PK sample is the same as 24 hours ( $\pm$  2h) C1D15 post-dose PK sample; it will be collected immediately prior the administration of DS-1594b.

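### Section 8.4 sets tau at 12 hours for the accumulation ratio and effective half-life; for once-daily subjects this would roughly halve the reported effective half-life, a descriptive parameter

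*Combined protocol and SAP*

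**What the plan says.** Two footnotes in Section 8.4 (PK Assessment) matter. The first reads "Accumulation ratio (AR) calculated as AUCltau at steady state /AUCltau following first dose", and continues "where tau is the dosing interval of 12 hour". The second says "Effective half-life can be calculated from AR" and gives ln2·tau/ln(AR/(AR−1)), with no separate value for tau. Both parameters are listed for Cycle 1 Day 8 in dose escalation and dose expansion, without restriction to BID subjects.

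The starting regimen is BID. Section 3.2 states: "The first dose cohort will start at 70 mg twice daily, approximately every 12 hours". QD is nevertheless a planned alternative. Section 3.1 lets the Safety Review Committee (SRC) switch to QD or run both regimens at once, and Section 5.1.1 adds: "BID and QD cohorts can be enrolled in parallel and will be evaluated independently for DLT".

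The sampling tables separate the two regimens. Table 14 (BID) has a 12-hour sample on the full-profile days. Table 15 (QD) stops at 8 hours and resumes at the next morning's pre-dose draw, with the footnote "Predose C1D2 PK sample is the same as 24 hours" after the Day 1 dose. It has a matching footnote for Day 8.

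Table 2 lists AR among the secondary PK endpoints. Section 9.4.9 summarises AR by geometric mean and the effective half-life (t1/2,ar) by median and range.

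**The concern.** Tau should be the interval between doses in the subject being analysed. The 12-hour figure is true for BID and false for QD, and nothing else in the plan corrects it. Because the effective half-life formula multiplies by tau, a wrong tau passes straight into the result.

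What is at stake is the comparability of one reported parameter. If both regimens are enrolled and the footnotes are followed as written, the summary would give the same drug two effective half-lives that differ by a factor of about two. The difference would come from the definition alone. A 12-hour AUC for QD subjects would also have to be interpolated between the 8-hour and 24-hour samples.

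**Working it through.** **Inputs.** Tau of 12 h and the formula t1/2,ar = ln2·tau/ln(AR/(AR−1)) come from Section 8.4. For the half-life, Section 3.1 says "the estimated clinical half-life of DS-1594b is ~ 7 to 8 hours". The true interval is 24 h divided by doses per day: 12 h for BID, 24 h for QD. The documents give no absorption rate constant (ka), so I assume 0.3 to 5 per hour.

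**Step 1: is the formula sound?** The plan states no AR or effective half-life value, so there is no figure to reproduce. For a one-compartment model with instantaneous input, AR = 1/(1−exp(−k·tau)) with k = ln2/t1/2. Then AR/(AR−1) = exp(k·tau), and the formula returns ln2/k, the true half-life, provided its tau is the actual dosing interval.

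**Step 2: both regimens, instantaneous input.**

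| True t1/2 (h) | BID AR | BID result, tau = 12 (h) | QD AR | QD result, tau = 24 (h) | QD result, tau = 12 (h) |
|---|---|---|---|---|---|
| 7 | 1.438 | 7.0 | 1.102 | 7.0 | 3.5 |
| 7.5 | 1.492 | 7.5 | 1.122 | 7.5 | 3.75 |
| 8 | 1.547 | 8.0 | 1.143 | 8.0 | 4.0 |

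For example, at 8 h under QD, exp(−k·24) = 2^(−3) = 0.125, so AR = 1/0.875 = 1.143 and AR/(AR−1) = 8. Then 24·ln2/ln8 = 8 h, while 12·ln2/ln8 = 4 h. At any given AR the ratio is 12/24 = 0.50.

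**Step 3: tau = 12 also used as the AUC window under QD.** For a one-compartment model with first-order absorption, AUC over 0 to T after the first dose is proportional to (1−e^(−kT))/k − (1−e^(−ka·T))/ka. At QD steady state the first term is divided by (1−e^(−24k)) and the second by (1−e^(−24ka)). At a half-life of 7.5 h:

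| ka (per h) | AR over 0–24 h | AR over 0–12 h | t1/2,ar, 24 h throughout (h) | t1/2,ar, 12 h throughout (h) | Ratio |
|---|---|---|---|---|---|
| 0.3 | 1.186 | 1.220 | 8.98 | 4.86 | 0.54 |
| 1 | 1.136 | 1.142 | 7.84 | 3.99 | 0.51 |
| 5 | 1.125 | 1.126 | 7.56 | 3.79 | 0.50 |

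For half-lives of 7 to 8 h across the whole ka range, the ratio stays between 0.50 and 0.54. AR moves by about 3% at most (1.252 against 1.213 at 8 h and ka = 0.3).

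**The case against.** The best defence is that this is wording left over from the BID starting schedule. The footnote calls tau the dosing interval, and the QD sampling is plainly built on 24 hours. Table 15 has no 12-hour draw and labels the next pre-dose sample as the 24-hour one. Tables 17 to 19 mark 12-hour samples as BID only and next-day pre-dose samples on the full-profile days as daily dosing only. An analyst guided by the sampling plan would probably use 24 hours, and the effective half-life footnote is permissive. This stands as a limit: the halving occurs only if the 12-hour figure is applied literally. It does not remove the point, because using 24 hours departs from the only numerical definition the plan gives.

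A reader might infer that the error would make QD look twice as fast to clear and so sway the choice between regimens. The documents do not support that. Section 3.1 has the SRC weigh all available clinical data and does not name t1/2,ar. Its case for BID rests first on lowering Cmax because of QT risk, and the half-life it adds is a projected clinical value, not one derived from AR. Section 8.4 lists CLss/F and a Kel-based half-life separately (the latter where calculable), and Section 9.4.9 plans a population PK fit. A value of 3.5 to 4 hours beside these would stand out.

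The parameter is also fragile under QD with the right tau. If AR were 10% off, taken here as an illustration, the result at a true 7.5 h would be about 3.6 or 10.0 h. That is a further reason not to suppose it drives decisions.

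**Conclusion.** The definition is wrong for QD subjects and should be corrected; its consequence is small. Read literally, it gives half the correct t1/2,ar at a given AR, or about 0.50 to 0.54 of the 24-hour value if the AUC window is shortened as well. These figures rest on the plan's 7 to 8 hour half-life, a one-compartment model and, for the second range, the assumed absorption rates. The exact halving at a given AR needs none of these assumptions.

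The damage is limited to a descriptive summary. Table 2 lists AR and t1/2 but not t1/2,ar. No BOIN rule or primary endpoint uses AR or t1/2,ar, and neither do the food-effect and DDI comparisons, which rest on AUCtau and Cmax. A reader might extend the problem to AUCtau and CLss/F in QD subjects. The text does not establish that, since the 12-hour value appears only in the AR footnote and the QD sampling points to 24 hours. It does justify stating the interval for AUCtau too.

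**What to change.** In both Section 8.4 footnotes, and wherever AUCtau is defined, state that tau is the subject's actual dosing interval: 12 hours for BID and 24 hours for QD. Section 9.4.9 takes its parameters from Section 8.4, so the correction carries through. The cost is one phrase. No samples are added, because Table 15 already provides the 24-hour draw, and no clinical procedure changes.
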